4.4 Trial Design

This will be an investigator-initiated, prospective, open label, parallel group, multi-center, randomized controlled trial (RCT). Participants will be randomized in a 1:1-ratio, using stratified (local) randomization by study center (UZ Leuven or AZ Sint-Lucas Brugge), to either a control group or an intervention group (n = 120 participants in total, 60 in each group). The randomization schedule will be based on center-specific, computer-generated sequences programmed in Research Electronic Data Capture (REDCap), ensuring allocation concealment.

Following randomization, the intervention group will be re-randomized (via computer-generated simple randomization in REDCap) into two arms in a 1:1 ratio (n = 30 participants in each arm).

Participants in intervention arm A will be asked to complete the RAID questionnaire once a week via the Sidekick app, compared to once a month in intervention arm B.

The control group will be followed according to usual care standards. This includes informal screening for psychosocial wellbeing and illness perceptions during outpatient clinic visits, with referral to specific allied health professionals for additional education or non-pharmacological support if needed. The scores derived from questionnaires that form part of the study design can be

[figure not shown]
used as a guide for these discussions. As part of standard care, participants in both the control group and the intervention group will also receive a standardized educational leaflet about RA (attached as additional file), as is already available in the clinic and via the website of patient organization **ReumaNet**.

In addition to usual care, participants in the intervention group will receive unrestricted, free-of-charge and unincentivized access to the Sidekick Health application. The application was designed by the company Sidekick Health (Iceland) with the support of pharmaceutical company Pfizer for the adaptation of the app to the Belgian public, with a design centered particularly around promoting behavioral change and a strong focus on gamification techniques. It includes an educational module (Appendix A) that was specifically developed for patients with RA in collaboration with 10 rheumatologists. In addition, the app allows users to record nutritional diaries, subjective sleep quality and physical activity (manually or through wearable activity trackers or the smartphone's accelerometer), while also providing several physical and mindfulness-based exercises and the option to record PROs such as the RAID questionnaire. Reminders or alerts can be set up and customized by the users in the app itself, according to their personal preferences. These logs are stored in the application's designated data cloud, from which all identifiable data will be removed upon termination of the account at the end of the study (also see section on Data handling). The educational program on the app runs for a period of 16 weeks.

In all groups, an in-person visit will be scheduled at baseline and after 16 weeks, with a window of 2 weeks before and 2 weeks after this time point, taking place at the Rheumatology outpatient clinic of the participating centers. At the baseline and week $16 \pm 2w$ visits and in all groups, we will collect routine clinical data, including clinical examination and readily available blood samples, DAS28-CRP/SDAI, and HAQ, as well as trial questionnaires in the form of the ASES, PCS, IPAQ-S, and PSQI (see 3.5 and 3.6). The following data will only be collected at baseline, also in all groups: RA phenotype (RF/ACPA/erosive), disease duration, past and current DMARD-therapy, comorbidities if present, educational level, and participants' demographic characteristics.

After the week $16 \pm 2w$ visit, the study ends, and all participants will be free to continue with the Sidekick-application at their leisure, by creating a personal account. As outlined in the section on Data Handling, the pseudonymized study account will be terminated at the end of the study, upon which all stored personal data will be removed from the application's data cloud. The aforementioned logged data and in-app data will be stored by Sidekick Health on a secure platform and provided in pseudonymized form as data for the study (also see section on Data handling), only identifiable through participants' study ID.

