6.1 By visit

Visit 1 (screening and baseline):

- Recruitment of eligible participants after informed consent at the Rheumatology outpatient clinic of the participating centers.
- Two-step randomization, as described above, into a control group and an intervention group (1:1), which will in turn be re-randomized in a 1:1 ratio into a weekly RAID arm and a monthly RAID arm.
- Downloading Sidekick Health app (intervention group only).
- Collection of demographic and disease-related characteristics for included patients: age, sex, RF and ACPA status, radiographic erosions, disease duration, current DMARD-therapy, prior DMARD-therapy, BMI, smoking status, education level.
- Collection of relevant medical and surgical history and comorbidities.
- Physical examination, including TJC28 and SJC28, measurement of weight and height.
- Patient's and Physician's global assessment (VAS).

- Participants in both the control and intervention groups will be asked to complete the following questionnaires considering self-efficacy (ASES), patient-reported outcomes (RAID), daily functioning (HAQ), pain catastrophizing (PCS), physical activity (IPAQ-S) and sleep quality (PSQI). Questionnaires will be completed in MyNexuzHealth (an online patient communication platform used by the University Hospitals Leuven Belgium) or, if not possible, in a pen-and-paper form at the outpatient clinic.

- Self-efficacy: The ASES is a patient-reported questionnaire (25) consisting of 20 items to measure one's arthritis-specific self-efficacy across 2 subscales: self-efficacy for managing pain (PSE, range 5-50), and self-efficacy for controlling other symptoms (OSE, range 6-60). Both scores can be summed to derive a total ASES-score (range 11-110).
- Patient-reported outcomes: The RAID questionnaire is a patient-derived differentially weighted 7-item tool assessing pain, functional disability, fatigue, sleep, coping, physical and emotional well-being.
- Daily functioning: The HAQ is a self-administered questionnaire, that assesses the ability in performing daily life activities and measures the functional impact of rheumatoid arthritis (26). The HAQ is routinely collected at the rheumatology outpatient clinic at University Hospitals Leuven.

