9.2 Analysis

Analyses will be carried out according to the intention-to-treat (ITT) principle, implying that participants will be analyzed based on the group they were originally assigned to.

In this study, the ITT population will consist specifically of all patients in the intervention group who effectively downloaded and installed the Sidekick application at the baseline visit, and all patients assigned to the control group. As stated above, participants in the intervention group will be re-randomized to intervention arm A or B, constituting two additional ITT populations that will only be analyzed exploratorily.

Per protocol (PP) analyses will be carried out as sensitivity analyses, including only those patients who completed the follow-up visit.

The variables described above in sections 4-6 will be extracted from the electronic medical patient file that is employed in all participating centers (KWS). Additionally, user behavior statistics and data actively logged by the patients in the app will be collected and provided for analysis in pseudonymized form by Sidekick Health. The primary and secondary outcome data of this study will be collected via questionnaires on the MyNexuzHealth app, or if not possible in pen-and-paper format at the outpatient clinic. All study-related information will be assembled and prepared for further analysis in an electronic CRF developed in REDCap. P-values <0.05 will be considered as statistically significant for all analyses. Missing data will be handled with multiple imputation by chained equations when data can be assumed to be missing at random. Descriptive statistics for baseline participant characteristics will be provided as means (\pm SD), medians (IQR) or proportions depending on data distribution.

Primary endpoint

The difference in mean change of total ASES (Arthritis Self-Efficacy Scale) score from baseline to week 16 \pm 2w in the intervention group when compared to the control group will be evaluated with an unpaired t-test or Wilcoxon rank sum test depending on distribution of the ASES-score. As a sensitivity analysis, we will additionally assess the difference between groups in week 16 scores using ANOVA adjusted for the baseline score. Furthermore, differences in the pain and other symptoms subscales of the ASES will be presented separately.

Secondary endpoints

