- The difference in mean change of total PCS score from baseline to week 16 \pm 2w in the intervention group will be compared to that in the control group, using an unpaired t-test or Wilcoxon rank sum test depending on distribution of the PCS score. As a sensitivity analysis, we will additionally assess the difference between groups in week 16 scores using ANOVA adjusted for the baseline score.

Exploratory endpoints

- The difference in mean change of total ASES score from baseline to week 16 \pm 2w in the intervention arm with weekly RAID questionnaires will be compared to that in the intervention arm with monthly RAID questionnaires, using an unpaired t-test or Wilcoxon rank sum test depending on distribution of the ASES-score. As a sensitivity analysis, we will additionally assess the difference between groups in week 16 scores using ANOVA adjusted for the baseline score.

- The difference in mean change of total PCS score from baseline to week 16 \pm 2w in the intervention arm with weekly RAID questionnaires will be compared to that in the intervention arm with monthly RAID questionnaires, using an unpaired t-test or Wilcoxon rank sum test depending on distribution of

the PCS score. As a sensitivity analysis, we will additionally assess the difference between groups in week 16 scores using ANOVA adjusted for the baseline score.

- The difference in mean change of total IPAQ-S score from baseline to week 16 ± 2w in the intervention group when compared to the control group will be evaluated with an unpaired t-test or Wilcoxon rank sum test depending on distribution of the IPAQ-S score. As a sensitivity analysis, we will additionally assess the difference between groups in week 16 scores using ANOVA adjusted for the baseline score.
- The difference in mean change of total PSQI score from baseline to 16 ± 2w in the intervention group when compared to the control group will be evaluated with an unpaired t-test or Wilcoxon rank sum test depending on distribution of the PSQI score. As a sensitivity analysis, we will additionally assess the difference between groups in week 16 scores using ANOVA adjusted for the baseline score.

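### Centre stratifies the intervention-versus-control randomisation but enters neither the ASES nor the PCS comparison; adding it is cheap, and the gain in precision is conditional and probably small.

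*Combined protocol and SAP*

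**What the plan says.** Section 4.4 makes centre a design factor for the main allocation, "using stratified (local) randomization by study center (UZ Leuven or AZ Sint-Lucas Brugge"), and describes how: "The randomization schedule will be based on center-specific, computer-generated sequences programmed in Research Electronic Data Capture (REDCap"). It mentions neither blocks nor a block size. The later split of the intervention group is a different procedure, in which participants are "re-randomized (via computer-generated simple randomization in REDCap) into two arms in a 1:1 ratio".

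In section 9.2 the change in total ASES "will be evaluated with an unpaired t-test or Wilcoxon rank sum test depending on distribution of the ASES-score". The change in total PCS is compared "using an unpaired t-test or Wilcoxon rank sum test depending on distribution of the PCS score". For both outcomes the sensitivity analysis assesses the "difference between groups in week 16 scores using ANOVA adjusted for the baseline score". Centre is not named in any test, regression model, mixed model or imputation statement in section 9.2. Under section 9.1, PCS non-inferiority is judged by the upper bound of a 95% confidence interval against a margin of 7.7.

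**The concern.** Stratifying by a factor related to the outcome removes its contribution from the true sampling error of the group contrast, provided the groups are balanced within strata. A test that ignores the factor still counts that variation as noise. Its standard error is then larger than it should be, its type I error falls below nominal, and some power is lost. Without enforced balance, the unadjusted test keeps its nominal error rate, but a chance difference in site mix between the groups moves the estimate. Either way, the plan stratifies by centre and then analyses as if it had not. At stake are a little power for ASES and a little width in the PCS interval that is compared with 7.7.

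**Working it through.** **Inputs from the documents.** ASES difference 5.5 and SD 9.4; two-sided alpha 0.05; 80% power; dropout 10%; 15% added for rank tests; N = 120, so 108 evaluable or 54 per group (section 9.1, Appendix B). PCS SD 12.3 and margin 7.7 (section 9.1).

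**Reproducing the plan.**
- ASES: d = 5.5/9.4 = 0.585 gives 46.8 per group, 94 in total. 94 × 1.10 = 103.4 (52 per group), and × 1.15 = 119, planned as 120.
- ASES power with 54 per group: 85.4% (t-test).
- PCS power with 54 per group at one-sided 0.025: Φ(7.7/(12.3 × √(2/54)) − 1.96) = Φ(3.253 − 1.96) = 90.2%, as stated.

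**Assumptions.** Allocation is balanced within centre. R² is the share of the variance in 16-week change that is due to centre; the documents give no value, so 0.02 and 0.05 are shown.

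**Formulas.**
- Excess in the unadjusted SE: 1/√(1 − R²) − 1.
- True type I error of the unadjusted test: 2 × (1 − Φ(1.96/√(1 − R²))).
- Adjusted ASES power: t-test power at d/√(1 − R²), 54 per group.
- Adjusted PCS power: Φ(3.253/√(1 − R²) − 1.96).
- PCS 95% half-width: 1.96 × 12.3 × √(2/54) = 4.64 unadjusted; multiply by √(1 − R²) for adjusted.

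| | R² = 0 | R² = 0.02 | R² = 0.05 |
|---|---|---|---|
| Excess SE | 0 | 1.0% | 2.6% |
| True type I error, unadjusted | 5.0% | 4.8% | 4.4% |
| ASES power with centre term | 85.4% | 86.1% | 87.1% |
| PCS power with centre term | 90.2% | 90.8% | 91.6% |
| PCS half-width with centre term | 4.64 | 4.59 | 4.52 |

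The 85.4% is the textbook figure for the unadjusted test. Under enforced balance that test does slightly better than this, because its true sampling error is smaller than the SE it uses. At R² = 0.05, using t-based values, its power is about 86.0%, so the like-for-like gain is about 1.1 points (87.1 − 86.0).

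**What R² means in points.** With share p of participants at one site, the site difference in change is 9.4 × √(R²/(p(1 − p))). For assumed splits from 50:50 to 80:28 (p = 0.50 to 0.74), R² = 0.02 needs 2.7 to 3.0 points and R² = 0.05 needs 4.2 to 4.8 points.

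**Simulation check** (assumed: 72 and 36 evaluable participants at the two sites, site difference in change of 0.5 within-site SD).
- Blocks of four: the unadjusted interval is 1.028 times as wide; type I error 4.2% unadjusted against 5.0% adjusted; power 84.5% against 85.8%.
- Unblocked: type I error 4.9% unadjusted against 5.0% adjusted; power 82.0% against 84.2%.
- No site difference, blocked: the two analyses agree (width ratio 1.000).

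**The case against.** The strongest reply is that nothing is shown to be wrong with the planned intervals. Excess width needs both enforced balance and a real site difference, and the documents establish neither. Where the error exists it is conservative, and unadjusted power already exceeds 80% for both endpoints. This stands, and it limits the point to efficiency.

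The endpoint is also a change score. A stable difference between sites in level or questionnaire mode largely cancels from baseline to week 16, and only a site difference in change counts in the main test. R² = 0.10 would give a 5.4% excess in SE, but it needs the sites to differ in change by 5.9 to 6.8 points. That is more than the 5.5 points the trial is designed to detect, and nothing in the documents supports it.

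Three stronger readings are tempting but not supported:
- A reader might infer a site difference from section 6.1, which says "The HAQ is routinely collected at the rheumatology outpatient clinic at University Hospitals Leuven" and describes the online questionnaire platform as one used at Leuven. HAQ is not an outcome in any planned group comparison, and sections 4.4 and 4.6 require it at both visits in all groups. Section 9.2 applies the same rule (platform first, paper if not possible) to all participants, and sections 6.1 and 9.2 describe a patient-record system shared by the centres.
- A reader might extend the point to the weekly-versus-monthly comparisons. Those arms come from simple randomisation, so leaving centre out ignores no design stratum there.
- A reader might count both conservatism and site imbalance as harms. They belong to different cases: balance within centre rules out the imbalance, and lack of enforced balance removes the conservatism.

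**Conclusion.** The omission is confirmed: the plan stratifies the intervention-versus-control allocation by centre and never uses centre in analysing it. The consequence is minor and conditional. With balance within centre and R² of 0.02 to 0.05, the unadjusted SE is about 1.0% to 2.6% too wide, type I error is about 4.8% to 4.4%, and ASES power rises from a planned 85.4% to 86.1% to 87.1%. If the sequences are unblocked, type I error is nominal, and adjustment still removes chance site imbalance and recovers precision where sites differ. If sites do not differ in change, the gain is zero. R², the site split and the use of blocks are all assumptions. The SD of 9.4 is applied to change only because the plan does so. No conclusion of the trial is shown to be at risk.

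**What to change.** In section 9.2, for the intervention-versus-control ASES and PCS comparisons, specify a linear model with group and centre (two levels, fixed effect), adding the baseline score in the adjusted version. If the rank route is taken, use the van Elteren test stratified by centre. That test yields a p-value only, so the linear model should supply the PCS interval that is set against 7.7. Include centre in the imputation model so that it matches the analysis. State in section 4.4 whether the centre-specific sequences are blocked.

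The cost is one degree of freedom. Centre is already known for every participant, N stays at 120, and no trial procedure changes. Fixing this before analysis also prevents a later data-driven choice about adjusting for centre.

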4.5 Study diagram

RAID = Rheumatoid Arthritis Impact of Disease ; q1w = once a week ; q1m = once a month ; DAS28 = Disease Activity Score 28 joints ; SDAI = Simple Disease Activity Index ; CDAI = Clinical Disease Activity Index ; ASEs =: Arthritis Self-Efficacy Scale ; IPAQ-S = International Physical Activity Questionnaire short form ; PSQI = Pittsburgh Sleep Quality Index ; HAQ = Health Assessment Questionnaire ; RF = rheumatoid factor ; ACPA = anti-citrullinated peptide antibodies ; DMARD = disease-modifying antirheumatic drugs ; BMI = body mass index

4.6 Trial Flowchart

Procedures / Assessment	Screening and randomization	Intervention period	
		During intervention	Visit 2 = Evaluation of primary endpoint
Visits / Contacts	Visit 1 = Baseline	During intervention	Visit 2 = Evaluation of primary endpoint
Timing (weeks)	Week 0		Week 16 ± 2w
Informed consent	X		
Inclusion / Exclusion criteria	X		
Randomization	X		
Downloading Sidekick Health app	X		
Demographics (age, sex), RF and ACPA status, radiographic erosions, disease duration, past and current DMARD-therapy, prior DMARD-therapy, BMI, smoking status, education level	X		
Medical and Surgical history, comorbidities (if available in the patient file)	X		
Physical examination (including TJC28 and SJC28)	X		X

Patient's global assessment (VAS)	X		X
Physician's global assessment (VAS)	X		X
HAQ	X		X
Weight / Height / BMI	X		X
Blood sampling (CRP) as part of usual care (in clinic or through patient's general practitioner)	X		X
ASES	X		X
PCS	X		X
IPAQ-S	X		X
PSQI	X		X
RAID (both control- and intervention group)	X		X
RAID (via Sidekick Health app, only in intervention group): - Intervention arm A: weekly - Intervention arm B: monthly		X	
Collecting in-app logged data concerning physical activity, sleep, diet, stress management			X

RF = Rheumatoid Factor, ACPA = Anti-citrullinated peptide antibodies, DMARD = disease-modifying antirheumatic drug, BMI = body mass index, TJC28 = tender joint count in 28 joints, SJC28 = swollen joint count in 28 joints, VAS = Visual Analogue Scale, HAQ = Health Assessment Questionnaire, CRP = C-reactive protein, ASES = Arthritis Self-Efficacy Scale, PCS = Pain Catastrophizing Scale, IPAQ-S = International Physical Activity Questionnaire short form, PSQI = Pittsburgh Sleep Quality Index, RAID = Rheumatoid Arthritis Impact of Disease

5. Selection and withdrawal of subjects

5.1 Inclusion criteria

Patients enrolled in the study must meet all of the following inclusion criteria:

1. Voluntary written informed consent of the participant or their legally authorized representative has been obtained prior to any screening procedures.
2. Are aged 18 years or older.
3. Have a diagnosis of RA, diagnosed by a rheumatologist, with a minimal disease duration of 16 weeks or more. This minimal disease duration was chosen based on conceptual reasons and previous work of our research group, suggesting that the dynamic and impactful first weeks after diagnosis are not the ideal time window to assess psychosocial outcomes (6).
4. Are able to understand and write Dutch.
5. Have access to a smartphone with an Android (requires Android 7.0 or later) or Apple iOS (requires iOS 13.0 or later) operating system.

All participants that are considered for Trial participation, per the above criteria will be documented on the Screening Log, including Screen Failures.

5.2 Exclusion criteria

Since the study intervention does not include an IMP, no strict exclusion criteria are defined other than the abovementioned inclusion criteria. However, participants will be excluded from analyses if they do not provide any questionnaire data at either of the two study visits, or, for the intervention group, if they fail to use the Sidekick Health application at least once (= dropouts).

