Study population	
Patients diagnosed with rheumatoid arthritis aged 18 years or older, with a disease duration of 16 weeks or more, no exclusions based on sex or therapy.
 
Patients will be randomized (1:1) to one of the following groups:
 
 - Control group: standard of care (including referral to allied health professionals for additional education/non-pharmacological support as needed), educational leaflet, completion of the RAID questionnaire at baseline and last study visit. No access to the Sidekick Health app, and no completion of the RAID questionnaire in between study visits. - Intervention group: standard of care (including referral to allied health professionals for additional education/non-pharmacological support as needed), educational leaflet and access to the Sidekick Health app, including completion of the RAID questionnaire via the app in between study visits. 
Participants who are randomized to the intervention group will be re-randomized in a 1:1-ratio to one of the following arms:
 
 - Intervention arm A: intervention with the Sidekick Health app as described above, and participants will be asked to complete a RAID questionnaire in-app once a week. - Intervention arm B: intervention with the Sidekick Health app as described above, and participants will be asked to complete a RAID questionnaire in-app once a month.
Trial Design	Investigator-initiated, open-label, parallel-group, multicenter randomized controlled trial (without IMP).
Endpoints	
Primary endpoint Difference in mean change of total ASES (Arthritis Self-Efficacy Scale) score from baseline to week $16 \pm 2w$ in the

intervention group when compared to the control group. The ASES is a patient-reported questionnaire consisting of 20 items to measure one's arthritis-specific self-efficacy across 2 subscales: self-efficacy for managing pain (PSE, range 5-50), and self-efficacy for controlling other symptoms (OSE, range 6-60). Both scores can be summed to derive a total ASES-score (range 11-110).

Secondary endpoints

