9.1 Sample size

For the primary outcome, we opted for a superiority design aiming to reject the null hypothesis that there would be no difference between the intervention and control groups in the change of the total ASES-score from baseline to week 16. Sample size calculation was based on the previously proposed minimal clinically important difference in the ASES-score, corresponding with a change of 5.5 on either the pain or other symptoms subscale (13,25). Moreover, in a recently published, large prospective study from our research group, including 379 patients with RA, the mean (\pm SD) self-efficacy for pain (PSE) was 31.8 (\pm 8.9) and self-efficacy for other symptoms (OSE) was 42.6 (\pm 9.4) (32). Based on a minimal clinically important difference of 5.5 and population SD of 9.4, an effect size of approximately 0.59 was assumed. Additionally, based on previous research and outpatient clinic attendance experience, we expect dropout rate to be maximally 10% (13,24,33). Following these assumptions and in the setting of a superiority trial, 52 participants are needed in each group to detect a clinically meaningful difference in either PSE or OSE with 80% power and a significance level

of 0.05, while allowing for a 10% dropout rate.

It should be noted that the ASES score was not fully normally distributed in our aforementioned prospective study, implying that non-parametric tests might be needed to analyze the primary outcome. Following a general rule of thumb, sample size was thus increased by 15% to account for the loss of power these non-parametric tests would imply(34). Consequently, a total of 120 participants are needed (60 in each group) for the analysis of the primary outcome, with 80% power and a significance level of 0.05.

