Appendix A. Short overview of educational content in Sidekick app

Appendix B. R script for sample size calculations

```
library(pwr)
library(epiR)

#---- Primary outcome: ASES
d <- 5.5/9.4
power <- pwr.t.test(d = d, sig.level = 0.05, power = 0.80, type = "two.sample", alternative =
"two.sided")
samplesize <- round(power$n * 2)

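### Sidekick use outside the study account is neither screened for at entry nor recorded in either arm, so any resulting dilution of the app-versus-no-app contrast would go unseen

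*Combined protocol and SAP*

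**What the plan says.** The control condition is set out in the Study Synopsis (Study population): "No access to the Sidekick Health app, and no completion of the RAID questionnaire in between study visits". Three features limit what the trial itself hands out. The research team distributes the licences (section 1), the download at Visit 1 is for the intervention group only (section 6.1), and study accounts run on a coded email address (section 13).

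Eligibility is silent on the app. The five criteria in section 5.1 cover consent, age, diagnosis and disease duration, Dutch, and a compatible smartphone. Section 5.2 then states that "no strict exclusion criteria are defined other than the abovementioned inclusion criteria".

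The flowchart (4.6) has one row for logged app data, "Collecting in-app logged data concerning physical activity, sleep, diet, stress management", at Visit 2. Section 4.4 describes these data as supplied by Sidekick Health under the participant's study ID. Neither the flowchart nor the visit lists in 6.1 ask anyone about Sidekick use before the trial or outside the study account.

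Section 4.4 mentions another route to the app, for the period after the week 16 visit: "all participants will be free to continue with the Sidekick-application at their leisure, by creating a personal account".

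In the analysis, app exposure matters in one arm only. Intervention patients who did not install the app (9.2) or never used it (5.2) are left out. All patients assigned to control stay in the ITT set, and the per-protocol set is defined by attendance at follow-up (9.2).

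**The concern.** The comparison of interest is app versus no app, in an open-label trial where everyone has a suitable phone. A current Sidekick user is eligible as the criteria stand, and use through a personal account would leave no trace in the trial data.

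Two kinds of patient could weaken the contrast, by different routes. An existing user carries the app's effect in the baseline score. Since the endpoint is change from baseline, that patient gains little if assigned to the app, so the loss comes through the intervention arm. A control who newly opens an account during the 16 weeks gains some of the app's effect, so the loss comes through the control arm.

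For ASES the result is lost power. For PCS, the non-inferiority test is there to exclude a negative effect of the app (sections 7 and 9.1). If there is such an effect, dilution makes it look smaller and a pass more likely. No planned analysis would reveal or remove either problem.

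**Working it through.** **Inputs.** From section 9.1 and Appendix B: ASES difference 5.5, SD 9.4, two-sided 0.05, 80% power; dropout 10%; a further 15% for non-parametric tests; PCS SD 12.3, margin 7.7, level 0.025, no true difference assumed. Evaluable per group: 60 × 0.90 = 54. The affected share c is not in the documents and is assumed.

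**The plan's own figures.**
- ASES: d = 5.5/9.4 = 0.585 needs 46.8 per group, 94 in total. 94 × 1.10 = 103.4 (52 per group), and 103.4 × 1.15 = 119, in line with the stated 120.
- PCS: the standard error is 12.3 × √(2/54) = 2.367. Power = Φ(7.7/2.367 − 1.96) = 90.2%, as stated. This uses 0.025 as a one-sided level.

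**Dilution model.** Let δ be the true effect. Suppose a share e of each arm are existing users with no further change, and a share s of controls are new self-enrollers who get the full effect. The mean change due to the app is (1 − e)δ in the intervention arm and sδ in the control arm. The expected difference is therefore (1 − e − s)δ = (1 − c)δ, with c = e + s. The SD is held fixed.

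**ASES.** The t-test has 54 per group and noncentrality [5.5(1 − c)/9.4] × √(54/2), which is 3.04, 2.89, 2.74 and 2.43 for c = 0, 5%, 10% and 20%. The allowance column divides 54 by 1.15. The last column repeats the Appendix B chain with the diluted difference.

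| c | Difference | t-test power | Power with 15% allowance | Total N by the plan's chain |
|---|---|---|---|---|
| 0 | 5.50 | 85.4% | 80.1% | 119 |
| 5% | 5.225 | 81.6% | 76.0% | 132 |
| 10% | 4.95 | 77.4% | 71.4% | 145 |
| 20% | 4.40 | 67.4% | 61.2% | 183 |

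**PCS.** The probability of declaring non-inferiority is Φ((7.7 − (1 − c)δ)/2.367 − 1.96), where positive δ means the app worsens PCS.

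| c | δ = +7.7 | δ = +4 | δ = 0 | δ = −4 |
|---|---|---|---|---|
| 0 | 2.5% | 34.6% | 90.2% | 99.86% |
| 5% | 3.6% | 37.7% | 90.2% | 99.81% |
| 10% | 5.1% | 41.0% | 90.2% | 99.76% |
| 20% | 9.5% | 47.7% | 90.2% | 99.59% |

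For example, at c = 10% and δ = 7.7: (7.7 − 6.93)/2.367 − 1.96 = −1.635, and Φ(−1.635) = 5.1%.

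**The case against.** The strongest reply is that the documents show no open route to the app during the trial. A reader might infer from the personal-account sentence in section 4.4 that controls could sign up at any time. That sentence concerns the period after the week 16 visit, and does not establish that an account can be opened earlier or without a licence. This objection stands: earlier access is an open question.

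A reader might also infer that nothing in the conduct of the trial protects the control condition. That is not so, given the team-held licences and the intervention-only download. These limit what the trial supplies, but they neither stop nor record use obtained elsewhere. An instruction to controls could also sit in the consent form, which is not among the pages reviewed, so its absence cannot be asserted.

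A third tempting reading is that any outside use tilts the PCS test towards a pass. The second table contradicts this. Under the plan's assumption of no difference the pass probability does not move, and with a true benefit it falls slightly. The tilt exists only under true harm.

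Finally, the size is illustrative. Full effect from unprompted use is an upper bound, and nothing in the documents supports a particular share. The 5.5 and 9.4 are subscale values, while the primary endpoint is the total ASES score, so the powers are those of the plan's own calculation and not strictly those of the primary comparison. All of this is accepted. It limits how strongly the point can be put, but does not supply the missing screen or record.

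**Conclusion.** The gap is real but narrow. The protocol's control condition has no entry screen for current or past Sidekick users and no record of use outside the study account in either arm, and no planned analysis would show such use. Whether it happens, and how often, cannot be judged from the documents.

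If it does, modest shares matter. Under the assumptions above, t-test power is still above 80% at 5% affected and below it at 10%. With the plan's own non-parametric allowance there is almost no slack, and power is already below 80% at 5%. The PCS false-pass rate about doubles at 10% affected, but only when the true harm equals the margin. This supports a low-cost improvement to eligibility and data collection. It does not show that the comparison is compromised.

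**What to change.** - In 5.2, add current or previous use of the Sidekick Health app as an exclusion.
- In 4.4, state whether the app can be obtained before week 16 without a study licence.
- At Visit 1, ask controls not to open an account before Visit 2, unless the consent form already does so.
- In 4.6 and 6.1, add one item at Visit 1 and Visit 2, in both arms, on Sidekick use outside the study account. Asking controls alone would miss existing users assigned to the app.
- In 9.2, keep everyone in the assigned group for the main analysis, report the proportion exposed by arm beside the ASES and PCS results, and add a PCS sensitivity analysis excluding exposed controls. Label it as a non-randomised comparison, because use after randomisation is not random.

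The cost is a minor amendment, one extra question per visit and a few existing users made ineligible. Section 5.3 places inclusion between June and December 2022 and this version is dated November 2022, so some patients may already be enrolled. For them the exclusion comes too late, but the Visit 2 item can still ask about use before and during the trial.
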